PROTOCOL

**Effect of Medium Chain Triglyceride Intake on Colonization of Preterm
Infants with *Candida***

January 12, 2018

I. Purpose and Background

Systemic candidiasis has become the fourth leading cause of hospital acquired sepsis in the United States, making these infections as common as those caused by enteric Gram-negative bacilli.[1] Premature neonates are an immunocompromised population that has seen a concurrent increase in the incidence of these serious fungal infections. A report of neonatal late-onset sepsis in the NICHD neonatal network identified fungi as the cause of 12% of these infections, with *Candida* species being the 2nd most common etiologic agent overall (after coagulase-negative *Staphylococcus*).² Further, infections with *C. albicans* carried a mortality rate of 44%.[2] Thus, despite the dramatic advances in neonatal intensive care and the availability of antifungal drug therapies, these infections still carry an unacceptably high cost in terms of morbidity and mortality.

Antifungal prophylaxis has been shown to reduce invasive fungal infections in neonatal intensive care units; indeed, it has been suggested that all NICUs caring for extremely preterm infants should use antifungal prophylaxis.[3] However, this strategy is associated with risks of drug toxicity and emergence of resistance to antifungal drugs. Alternative strategies to reduce colonization and invasive disease are therefore warranted. Colonization with *C. albicans* generally precedes the development of invasive infection, and the gastrointestinal tract is a common site of colonization.[4] In an adult mouse model of colonization, dietary fatty acids impact the level of *C. albicans* colonization. Crucially, dietary medium chain triglyceride (MCT) oil decreases *C. albicans* colonization.[5] MCT oil has been an ingredient in infant formula since the 1950's. In a pilot study, we found that dietary supplementation of preterm infants with MCT oil for 7 days reduced colonization in infants who received it but not in control infants (Arsenault, et al., submitted). This is the first evidence that MCT oil can decrease colonization in preterm infants who are at risk for invasive disease with this organism.

This protocol describes an observational, follow-up study in which we will examine whether the suppression of *Candida* colonization with dietary MCT supplementation will be maintained over a longer time period of supplementation. Data collected in this study will be used to further inform a future interventional trial in which MCT oil can be formally tested for its ability to reduce *Candida* colonization in premature infants at risk for disseminated candidiasis.

- Specific Aims:**
1. To determine the frequency, timing, level, and dietary risk factors of *Candida* species colonization in the gastrointestinal tracts of preterm infants.
 2. To examine whether dietary supplementation with MCT oil reduces gastrointestinal colonization by *Candida* species.

II. Characteristics of the Research Population

Any premature infant admitted to the Neonatal Intensive Care Unit (NICU) at Women and Infants Hospital will be eligible for this study. There will be no distinction based on gender or ethnicity. We anticipate that 800 different individuals will be adequate to provide the number of samples required for these experiments. Because we are interested in supplementing infants colonized with *Candida* with MCT oil, we will restrict the targeted group to those infants who are already receiving dietary supplements through either preterm or transitional formula or fortified breast milk. These infants are generally under 2000 grams birth weight.

Inclusion criteria: Any premature infant admitted to the NICU at Women & Infants Hospital who is on full enteral feeds of either preterm or transitional formula or fortified breast milk and who is anticipated to have a minimum stay of two weeks.

Exclusion criteria: Infants not on full enteral feeds with preterm formula or fortified breast milk or whose NICU stay is anticipated to be less than two weeks.

III. Methods and Procedures

1. Obtaining Specimens: Preterm infants admitted to the NICU will be screened for inclusion. Each medical record will be reviewed to confirm that the standard hospital consent form was signed on admission and that there were no exclusions indicated for the collection of stool for research purposes. A subject ID number will be assigned. Stool samples identified only by subject ID number will be collected and processed to determine whether they contain *Candida* species by standard laboratory methods in the [name] research laboratory. Because colonization with *Candida* may develop over time, we will collect stool samples from eligible patients weekly throughout their hospital stay. Parent(s) of colonized infants will be approached for informed consent. Once consent is obtained, infants will be randomized into control and supplementation groups. After baseline sample collection, infants in the supplementation group will receive 0.5 ml/oz additional MCT oil (4 kcal/oz) as a nutritional supplement for 21 days or until hospital discharge. Sample collection from enrolled infants will include a stool sample and 0.5 ml of maternal breast milk obtained from a bottle provided to the patient's room. Samples will be collected three times during the study period: before supplementation is started, 1 week after supplementation is started, and at the conclusion of the supplementation period.. The following information will be extracted from the medical record of consented infants: gestational age, birth weight, day of life, gender, admitting diagnosis, prenatal infection screening labs, method of delivery, antibiotic use (duration and drug class), corticosteroid use, presence of central lines, amount and types of feeds (breast milk only, breast milk and formula, formula only; formula brand; type and amount of fortifiers and other nutritional supplements) and feeding modality (breast, bottle, NG, G-tube) will be recorded. If any infant subsequently develops an invasive fungal infection or oral thrush, that will also be noted. All information extraction will conform to HIPAA and institutional standards for protected health information.

2. Data Analysis: Stool samples from preterm infants admitted to the ICU will be processed by standard laboratory methods in the [name] research laboratory to determine whether they contain *Candida* species. The presence and concentration of organisms will be recorded. Once infants are enrolled, stool samples and breast milk will be collected and stored for later testing at Tufts University. The presence and concentration of microbes in stool samples will be quantified, and the fatty acid content of breast milk samples will be analyzed. All identifiers will be removed from all samples collected for this study; they will be identified only by subject study ID number. No PHI will be provided to Tufts. Laboratory data generated from these studies will be maintained independent from any patient identifying information. Patient identifiers will be maintained in coded fashion secured in [name] office at Women & Infants Hospital. This office is in a building distinct from that of the laboratory.

Candida MCT

Microbiological Methods: Stool samples will be weighed and suspended in 10 ml of sterile saline. Serial dilutions will be cultured on YPD agar media (1% yeast extract, 2% peptone, 2% dextrose, 2% agar) containing 100 µg/mL streptomycin and 50 µg/mL ampicillin to inhibit bacterial growth and to allow quantification of the yeast content per gram of stool. Colonies will be evaluated by light microscopy to confirm that they are comprised of yeast. Yeast will be speciated using the FDA-approved Vitek-2 system.

3. Safety Assessments: Because MCT oil is already a component of infant formulas and breast milk, and because recommended dietary intakes will not be exceeded, there are no specific procedures, laboratory evaluations, or measures required to monitor infants receiving the supplement. Routine clinical care and assessments will be undertaken, with the option to discontinue the supplement in the unlikely event that there is any clinical suspicion of intolerance. In particular, enrolled patients receiving supplemental MCT oil will be monitored for the following signs/symptoms:

1. Feeding intolerance – defined as any clinical event related to feeding (gastric aspirates, emesis, abdominal distension) that results in a reduction or withholding of enteral feedings for a period of 24 hours or more.
2. Diarrhea
3. Necrotizing enterocolitis
4. Poor weight gain
5. Excessive weight gain

Adverse event

An adverse event is any untoward medical occurrence in a patient or trial subject administered a pharmaceutical product; the event does not necessarily have a causal relationship with the treatment or usage. Adverse events include the following:

- Abnormal test findings, as specified below.
- Clinically significant signs and symptoms.
- Changes in physical examination findings.
- Progression/worsening of underlying disease.

Abnormal test findings

An abnormal test finding, e.g., abnormal laboratory analysis results or vital signs, should be recorded as an adverse event in any of the following situations:

- The investigator considers the test result to be clinically significant.
- The test is associated with accompanying symptoms. Note, that the symptom, not the test result, should be recorded as an adverse event.
- The test result leads to a medical/surgical intervention including withdrawal of investigational product or discontinuation from the study. Repeat/confirmatory testing is not considered a medical intervention.

Serious adverse event (SAE)

An adverse event that meets one or more of the following criteria/outcomes is classified as serious:

- Results in death.
- Is life-threatening (i.e., at immediate risk of death).

Candida MCT

- Requires prolongation of hospitalization.
- Results in persistent or significant disability/incapacity.
- Other medically important adverse event that may not result in death, be life threatening, or require hospitalization may be considered serious when, based upon appropriate medical judgment, they may jeopardize the patient or may require medical or surgical intervention to prevent one of the outcomes listed above.

Adverse Event Grading Scale

The adjectives MILD, MODERATE, or SEVERE will be used to describe the maximum severity of the adverse event. For the purpose of consistency, these intensity grades are defined as follows:

- MILD: Does not interfere with patient's usual function.
- MODERATE: Interferes to some extent with patient's usual function.
- SEVERE: Interferes significantly with patient's usual function.

Note the distinction between the gravity (seriousness) and the intensity (severity) of an adverse event. **Severe** is a measure of intensity; thus, a **severe** reaction is not necessarily a **serious** reaction. For example, a headache may be severe in intensity, but would not be classified as serious unless it met one of the criteria for serious events listed above.

Causality assessment

For each adverse event, a causality assessment will be made to determine if there is a reasonable possibility that the investigational product caused the adverse event. The adverse event is assessed using the following classification and criteria:

Not related: This relationship suggests that there is no association between the investigational product and the reported event.

Unlikely: This relationship suggests that the temporal sequence of the clinical event, including a laboratory test abnormality, with investigational product administration makes a causal relationship improbable, and that other drugs or underlying diseases provide plausible explanations.

Possible: This relationship suggests that treatment with the investigational product caused or contributed to the adverse event, i.e., the event follows a reasonable temporal sequence from the time of drug administration or follows a known response pattern to the investigational product, but could also have been produced by other factors.

Probable: This relationship suggests that a reasonable temporal sequence of the event with investigational product administration exists and, based upon the known pharmacological action of the drug, known or previously reported adverse reactions to the drug or class of drugs, or judgment based on the investigator's clinical experience, the association of the event with the investigational product seems likely.

Definite: This relationship suggests that a definite causal relationship exists between investigational product administration and the adverse event, and other conditions (concurrent illness, progression/expression of disease state, or concurrent medication reaction) do not appear to explain the event.

“**Not related**” and “**unlikely**” will be included in the category “**unrelated**” (i.e., not having a reasonable suspected causal relationship to the investigational product).

“**Possible**”, “**probable**” and “**definite**” will be included in the category “**related**” (i.e., having a reasonable causal relationship to the investigational product).

IV. Risk/Benefit Assessment

This is a minimal risk study. Collection of stool samples presents no risk to the patient. The very small volume of breast milk that is required for research purposes will not impact that which is available to the baby, but in the event that there is any concern about breast milk supply, the samples will not be collected. Some babies will receive a supplement of MCT oil to their feedings. MCT oil is already a component of preterm formulas and is present to varying degrees in breast milk as well. It is commercially available and in routine use as a caloric supplement in premature infants. The amount of MCT oil that will be supplemented (4 kcal/oz) is within the range recommended and maintains the appropriate fat:total calorie ratio for infant feeding. Because colonization with *Candida* is a recognized risk factor for invasive candidiasis in premature infants, if MCT oil supplementation reduces colonization with this potential pathogen, the subjects could potentially benefit from participation.

Colonization of the gastrointestinal tract with *Candida* species is a very common occurrence in premature infants, occurring in 30-60% of infants in recent series. Determination of colonization status for *Candida* is not a part of routine clinical care. Although colonization has been defined as a risk factor in research settings, the vast majority of infants who are colonized with *Candida* species will not develop invasive disease. The infants who are found to have *Candida* in their stool therefore do not exceed a risk threshold that would warrant any specific treatment for this condition in current clinical practice.

V. Subject Identification, Recruitment, and Consent/Assent

Subjects will be identified by the investigators. The subject's hospital admission consent form will be reviewed to confirm that it has been signed and that the patient has not indicated any restrictions on the use of stool samples for research purposes.

There are no costs to the patient or financial incentives for the patient for participation in this study.

VI. References

1. Calderone, R.A., *Candida and Candidiasis*, 2002, ASM Press: Washington D.C.
2. Stoll, B.J., et al., *Late-onset sepsis in very low birth weight neonates: the experience of the NICHD Neonatal Research Network*. Pediatrics, 2002. **110**(2 Pt 1): p. 285-91.

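### The five tolerance events are monitored only in infants given MCT oil, so the randomized groups cannot be compared on them; the end sample also needs a time that does not depend on early stopping

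*Protocol*

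**What the plan says.** Protocol section I (Purpose and Background) states: "This protocol describes an observational, follow-up study". It leaves formal testing of MCT oil to a later interventional trial that these data are meant to inform. Section III.1 (Obtaining Specimens) then says that, after consent, "infants will be randomized into control and supplementation groups".

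On tolerance, section III.3 (Safety Assessments) says that "enrolled patients receiving supplemental MCT oil will be monitored for the following signs/symptoms" and lists five: feeding intolerance, diarrhea, necrotizing enterocolitis, poor weight gain and excessive weight gain. No matching sentence covers controls. The chart list in section III.1 does cover both groups, since it begins "The following information will be extracted from the medical record of consented infants", but none of the five is on it. The adverse-event definition that follows Safety Assessments refers to a subject who has been given a pharmaceutical product.

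On timing, the supplement is given "for 21 days or until hospital discharge". Enrolled infants are sampled three times: "before supplementation is started, 1 week after supplementation is started, and at the conclusion of the supplementation period". Safety Assessments allows a supplemented infant to stop, "with the option to discontinue the supplement in the unlikely event" of suspected intolerance. Separately from the three study samples, section III.1 says that colonization "may develop over time, we will collect stool samples from eligible patients weekly".

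**The concern.** Once infants are randomized, the value of the control group is that it shows what would have happened without the supplement. That holds for tolerance as much as for colonization. The five events can have causes other than MCT oil; the protocol's own causality scale allows for underlying disease and other drugs as explanations. A rate seen only in supplemented infants cannot separate the effect of the oil from the background rate in this population.

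This matters because the stated use of the data is to inform a later trial, and whether the supplement is tolerated is one of the things such a trial would need to know. Who is monitored and what is extracted are data-collection rules set in the protocol. An analysis plan cannot supply control events that were never recorded.

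The second issue is smaller. If the day of the last sample can move with early stopping, it can move only in the MCT group, and it then depends on tolerance. The study asks whether suppression of colonization lasts over a longer period, so the last sample carries much of the weight.

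**Working it through.** The protocol gives no figure to reproduce here. The main check sets its provisions side by side.

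| Item | Source | MCT group | Control group |
|---|---|---|---|
| Monitoring for the five events | III.3 | Stated | Not stated |
| Five events on the chart list | III.1 | 0 of 5 named | 0 of 5 named |
| Feed amounts and types | III.1 | Extracted | Extracted |
| Reason for a feed reduction | III.1 | Not listed | Not listed |
| Invasive fungal infection, oral thrush | III.1 | Noted | Noted |

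The chart list is the same for both groups. The asymmetry comes from the monitoring sentence alone, and the chart list does not make it good. The fourth row matters because the protocol defines feeding intolerance as a feeding-related event that leads to feeds being reduced or withheld for at least 24 hours. Feed amounts may show a reduction, but not whether a feeding-related event caused it. The last row shows that the protocol writes recording for any infant where it wants it.

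**What recording both groups would give (illustrative).** Inputs are assumptions: event rate p of 10%, 20% or 30%, the same in both groups, and n of 50 or 200 per group. The 95% half-width of the difference is 1.96 × √(2p(1−p)/n).

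- p = 0.20: n = 50 gives 1.96 × 0.080 = 15.7 points; n = 200 gives 1.96 × 0.040 = 7.8 points.
- p = 0.10: 1.96 × 0.060 = 11.8 points and 1.96 × 0.030 = 5.9 points.
- p = 0.30: 1.96 × 0.0917 = 18.0 points and 1.96 × 0.0458 = 9.0 points.

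So the estimate would be rough to moderately precise, 5.9 to 18.0 points either way. With controls unrecorded there is no estimate of the difference at all.

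**End-sample timing (illustrative).** Let T be the day a control gives the last sample and d the day an MCT infant stops. If the sample is taken at stopping, the gap is T − d. Take d from 3 to 14, and 5% to 20% of MCT infants stopping; all of these are assumptions.

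- T = 21: the gap is 21 − 14 = 7 to 21 − 3 = 18 days in an infant who stops. Averaged over the MCT group it is 0.05 × 7 = 0.35 to 0.20 × 18 = 3.6 days.
- T = 14 (discharge at the two-week stay that section II takes as its minimum): the gap is 14 − 14 = 0 to 14 − 3 = 11 days. The group average is 0 to 0.20 × 11 = 2.2 days.

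The result depends on the discharge day and on a stopping rate that the protocol does not give. It shows that the ambiguity can move the sample; it does not predict by how much.

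**The case against.** Much can be said for the protocol.

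- **Comparing safety is not an aim.** The two aims concern colonization only. The five events come straight after the option to discontinue, which only MCT infants have, and the section otherwise relies on routine care, which controls also receive. This stands as an explanation of why the list was written that way, and some control events will be in the clinical charts. But no planned step captures them, so the study data remain one-sided.
- **The adverse-event wording is generic.** A reader might infer that it deliberately excludes controls. It does not show that: MCT oil is described as a nutritional supplement, so a literal reading would not clearly cover the MCT group either. The wording needs tidying and is not independent proof of unequal recording.
- **Controls are sampled.** A reader might infer that controls have no end sample. The text does not support this. Controls are enrolled infants, all three samples are due from them, and 21 days or discharge is the natural shared calendar. What remains is the MCT infant who stops early, and only if the supplementation period is read as ending on the stopping day.
- **Weekly stools are collected regardless of group.** This stands and reduces the timing concern, since a stool near day 21 may exist for both groups. It does not remove it: the weekly stools are not linked to the end sample and do not include breast milk.
- **The label.** A reader might infer that calling the study observational undermines the randomization or produced the one-sided monitoring. The documents show the asymmetry, not its cause.

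**Conclusion.** The point holds for tolerance. All five listed events are monitored only in infants receiving MCT oil, and none is on the chart list shared by both groups, so the planned data do not allow a randomized comparison of tolerance. This rests on the text and needs no numerical assumption. The half-widths of 5.9 to 18.0 points rest on assumed rates and group sizes and only indicate what recording both groups would offer.

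The timing point holds in a narrow form: the end-sample day is ambiguous for MCT infants who stop early. The day counts above are illustrations. A gap of 7 to 18 days in particular should not be taken as the expected size, since it ignores discharge before day 21 and the protocol regards intolerance as unlikely. The observational label is a wording matter.

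None of this invalidates the colonization comparison. It is a specific weakness that is cheap to correct before data are collected.

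**What to change.** 1. In Safety Assessments, record the same five events in both randomized groups, with the same definitions and over the same window. Only feeding intolerance is defined at present; whatever definitions the investigators adopt for the other four should apply to both groups. Add the five events to the chart list in Obtaining Specimens.
2. Word the adverse-event definition so that it applies to any randomized infant.
3. In Obtaining Specimens, time the samples from baseline in both groups, keeping the protocol's own times: baseline, 1 week, and 21 days or discharge if earlier. State that this calendar applies whether or not the supplement was stopped.
4. In section I, reconcile the label with the randomization, for example by describing an observational screening cohort with an embedded exploratory randomized comparison.

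The cost is five added items in a chart extraction already done for all consented infants. No extra infants or samples are needed. Some MCT infants who stop early may give the last sample later than the present wording could imply. The change leaves the supplement, its duration and the decision to stop it as they are.

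### Tolerability events are to be monitored only in infants given MCT oil, so the randomized controls provide no like-for-like comparison

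*Protocol*

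**What the plan says.** Section III.1 (Obtaining Specimens) sets up a concurrent comparator: "Once consent is obtained, infants will be randomized into control and supplementation groups". It then lists the chart data for both groups, beginning "The following information will be extracted from the medical record of consented infants: gestational age, birth weight, day of life" and going on to diagnoses, antibiotics, steroids, lines, and the amount, type and route of feeds. The clinical events it adds for every infant are two: "If any infant subsequently develops an invasive fungal infection or oral thrush, that will also be noted".

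Section III.3 (Safety Assessments) first says that "there are no specific procedures, laboratory evaluations, or measures required to monitor infants receiving the supplement", and that routine care applies, with the option of stopping the supplement. It then names the group to be watched: "enrolled patients receiving supplemental MCT oil will be monitored for the following signs/symptoms". Five items follow: feeding intolerance, diarrhea, necrotizing enterocolitis, poor weight gain and excessive weight gain. Only feeding intolerance is defined.

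The adverse event text defines an event as "any untoward medical occurrence in a patient or trial subject administered a pharmaceutical product". The causality text asks whether "there is a reasonable possibility that the investigational product caused the adverse event".

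**The concern.** All five events can occur in preterm infants who receive no MCT oil. The definition of feeding intolerance (a feeding-related clinical event that leads to feeds being reduced or withheld for 24 hours or more) does not depend on exposure. The number of events in the supplemented arm is therefore background plus any effect of the oil, and a randomized control group is the direct way to separate the two.

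As written, the plan collects that number in one arm only. What remains is case-by-case causality judgement. Under the protocol's scheme, an event that other factors could have produced may still be rated possible, and possible counts as related. Background events can thus be counted as related with no control rate to set them against.

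Section I says the data will inform a future interventional trial. A comparative tolerability estimate would serve that trial, and the infants needed for it are already enrolled and randomized.

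**Working it through.** **1. Who is covered, section by section.** The protocol states no figure on this point, so the first check is textual.

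| Protocol text | Infants covered | Any of the five events? |
|---|---|---|
| III.1, chart extraction | all consented infants | No. Birth weight is the only weight; feed amounts are an indirect trace of feeding intolerance |
| III.1, events noted in any infant | all | No. Invasive fungal infection and oral thrush only |
| III.3, monitoring list | infants receiving MCT oil | Yes, all five |
| Adverse event definition | read literally, subjects given a product | Not listed |
| Causality assessment | judged against the product | Not listed |

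None of the five events is assigned to controls. Feeding intolerance might be partly rebuilt from feed amounts, but the definition also needs a triggering clinical event and the 24-hour duration. Neither weight-gain item can be derived from birth weight alone.

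**2. What a one-arm count can and cannot say.** All inputs here are assumed: 60 or 120 infants per arm, 30% feeding intolerance on MCT oil, and 10%, 20% or 30% in controls.

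The Wilson 95% interval for x events in n infants, with p = x/n and z = 1.96, is [p + z²/(2n) ± z√(p(1−p)/n + z²/(4n²))] / (1 + z²/n). For 18/60 it is 19.9% to 42.5%.

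For the difference d = p₁ − p₂, Newcombe's method takes the Wilson limits (l₁, u₁) and (l₂, u₂) of the two arms:

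- lower limit = d − √[(p₁ − l₁)² + (u₂ − p₂)²]
- upper limit = d + √[(u₁ − p₁)² + (p₂ − l₂)²]

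| Control rate | Difference (points) | 95% CI, 60 per arm (18 vs 6, 12, 18) | 95% CI, 120 per arm (36 vs 12, 24, 36) |
|---|---|---|---|
| 10% | +20 | +5.7 to +33.6 | +10.0 to +29.7 |
| 20% | +10 | −5.5 to +24.9 | −1.0 to +20.7 |
| 30% | 0 | −16.1 to +16.1 | −11.5 to +11.5 |

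The same supplemented-arm count fits all three rows. Only control data collected to the same definition can say which row applies.

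**3. Why later chart retrieval is not equivalent.** Suppose both arms have the same true rate p, every event is captured on MCT oil, and a fraction s is captured in controls. The apparent difference is p − sp = p(1 − s), and the apparent ratio is 1/s.

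| True rate in both arms | s = 0.6 | s = 0.9 |
|---|---|---|
| 10% | +4 points | +1 point |
| 20% | +8 points | +2 points |
| 30% | +12 points | +3 points |
| Ratio, any rate | 1/0.6 = 1.67 | 1/0.9 = 1.11 |

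The excess is false in every cell, because the true difference is zero.

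**The case against.** The strongest reply is that the list in section III.3 serves the option to stop the supplement. Controls have no supplement to stop, so naming only supplemented infants is natural, and the list is not presented as an outcome. Routine care reaches both arms, no special procedure is required even on MCT oil, and the method of monitoring in that arm is not described. Unequal ascertainment is therefore inferred from who is named, not stated outright. The extraction list omits the five events for both arms alike.

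Much of this is fair. Control charts will exist, a diagnosis such as necrotizing enterocolitis would probably appear in them, and nothing here shows that control events are unobservable. The adverse event wording looks generic: its example is a headache, and it speaks of a pharmaceutical product where section III.1 calls MCT oil a nutritional supplement. It should not be read as a decision to exclude controls. Tolerability is not a specific aim, and the arm sizes, rates and capture fractions above are assumed. At 120 per arm the interval for a 10-point difference still includes zero, so control data would not guarantee a clear answer.

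None of this brings controls into the monitoring. The restriction is written for this study, and no other section offsets it. An analysis plan can decide how events are tabulated by arm, but it cannot tabulate control events that were never collected on the same basis.

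**Conclusion.** The concern holds. The protocol names supplemented infants alone for monitoring of the five events and provides no equivalent recording in the randomized controls. Followed as written, it yields tolerability counts in one arm without a like-for-like comparator.

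The consequence is confined to safety; the colonization aims are unaffected. Its size cannot be fixed from the protocol. The figures above show that one plausible count could mean anything from no excess to 20 points, and that incomplete chart retrieval in controls could produce a false excess of 1 to 12 points over the assumed ranges. The textual finding does not depend on those assumptions. The change should be made because it is cheap and the comparator is already in place.

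**What to change.** - In section III.3, state that the five events, adverse events and serious adverse events are ascertained in all enrolled infants in both groups, with the same definitions and the same window from randomization.
- Word the adverse event definition to cover every enrolled infant.
- Add the five events and serial in-study weights to the extraction list in section III.1, and report events by randomized arm.
- Reconcile the sentence saying that no specific procedures or measures are needed with the monitoring list that follows it, for example by saying that the listed signs are observed within routine care.

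The cost is wording, plus modest extra abstraction and event reporting for controls whose records are already being reviewed. No new procedures or patients are needed, and no rule of clinical care changes.
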